## 10. INDEX PROCEDURE

### 10.1. INDEX BASELINE ANGIOGRAM

The Index Baseline Angiogram will be performed before Pre-Enrollment Balloon Angioplasty in order to assess baseline angiographic eligibility for inclusion as described in **Section 10.1.2** below. The angiogram is to be performed as per guidelines established by the independent core laboratory. Index procedure angiograms performed for all enrolled subjects will be reviewed by the core lab for specified data points (including identification of post-PTA dissections and associated type), as outlined in the angiographic core lab protocol.

#### 10.1.1. PREPARATION

Procedural techniques will be in accordance with the institutional standard of care for balloon angioplasty of the superficial femoral and proximal popliteal arteries.

All subjects should receive the appropriate antiplatelet therapy per Table 6. Study Medications above (**Section 9.2**).

All sites will receive study devices containing a 120cm length delivery catheter to facilitate either contralateral or ipsilateral vascular access, per operator discretion.

**Ruler Placement:** A radiopaque ruler is placed directly on the subject's target limb under the sterile drapes. The end of the ruler should be placed at the tibial plateau. In any later assessments, including follow-up duplex and X-Ray evaluations, the process will be repeated

to identify the treatment location. All other measurements are referenced back to this angiographic measurement.

Refer to the Instructions for Use (IFU) for a description of the procedure.

#### 10.1.2. BASELINE ANGIOGRAPHIC REQUIREMENTS

Baseline angiographic measurements of the target lesion (visual estimate) shall be captured to determine eligibility and include, but are not limited to the following:

- Target Lesion Location (Prox. SFA, Mid SFA, Distal SFA, Prox. Popliteal [P1])
- Baseline Lesion Length
- Lesion type (Single, Combination or Tandem / De novo or Non-stented restenotic)
- Reference Vessel Diameter (proximal and distal)
- Calcification Severity (None, Mild, Moderate or Severe)
- Baseline Diameter Stenosis (%)
  - Note: The number of subjects with total occlusions (100% occluded target lesion at baseline) will be closely monitored by the sponsor so as not to exceed 20% of subjects enrolled in the study. Once this rate has been reached, sites will be appropriately notified by the sponsor.
- Number of patent (<50% DS) infrapopliteal vessels to the ankle (must have at least one patent vessel that has not been revascularized to qualify for this study)
- Presence of thrombus

Subjects that are eligible for enrollment and present with bilateral stenosis (qualifying lesions in both limbs) may be enrolled under the following conditions:

- The more severe stenosis, per operator discretion, that is intended to be treated with only balloon angioplasty should be considered for enrollment.
- Per operator discretion, the non-target limb lesion can be treated by any appropriate clinical means other than the study device no less than 14 days prior to or 30 days after enrollment (Note: If the PI documents the need for planned intervention on contralateral limb at the time of the index procedure, it would not be considered an adverse event at time of occurrence if treated after enrollment, but this should not be less than 30 days post index procedure).

If subjects that are eligible for enrollment and present with bilateral stenosis are determined by the PI to require intervention during the same procedure, the subject should not be enrolled.

## 10.2. PRE-ENROLLMENT BALLOON ANGIOPLASTY

All consented subjects undergoing balloon angioplasty for possible enrollment into this study shall receive PTA treatment with a standard balloon or FDA-approved Lutonix drug-coated balloon.

Note: Requirements for pre-dilatation with a standard balloon (non-drug coated) preceding treatment with a DCB should be performed in accordance with the respective IFU. Once the DCB is introduced, inflations should be performed according to recommendations below for balloon angioplasty. Operators should follow these recommendations unless patient safety concerns present.

The recommendations for balloon inflation are as follows:

- The operator should select a balloon diameter that can be inflated to a ratio of 1.1:1 relative to the target lesion proximal RVD.
- The length of the balloon should be appropriate for the lesion length. When possible, a single balloon should be selected that extends across the entire lesion. If a DCB is being used, then the relevant instructions for use should be referenced for lesion lengths requiring multiple balloons.
- Balloon Inflation: Inflate the balloon and maintain inflation at the specified 1.1:1 diameter for a minimum of 60 seconds total (180 seconds is recommended).

Please refer to the Instructions for Use (IFU) for detailed instructions regarding Pre-Enrollment Balloon Angioplasty inflation recommendations.

### 10.2.1. POST-ANGIOPLASTY ANGIOGRAPHIC REQUIREMENTS

Final angiographic eligibility of subjects for study device treatment will be determined post pre-enrollment balloon angioplasty and include the following target lesion measurements (by visual estimate):

- Target lesion residual diameter stenosis <30%
- Presence of dissection(s)
- Presence of thrombus

In addition, other lesion measurements and balloon details will be recorded during Pre-Enrollment Balloon Angioplasty and include but are not limited to the following:

- Total number of dissection(s) visualized
- Dissection characteristics (by visual estimate) for each dissection visualized including:
  - Dissection Type (A through F)
  - Dissection Length
- Balloon Type (standard or drug-coated), Length, Diameter
- For each balloon inflation:
  - Inflation Duration(s) at Max Pressure

- Max Pressure (ATM)

### 10.3. STUDY DEVICE TREATMENT

Subjects that meet all inclusion and angiographic inclusion criteria, and do not meet any exclusion or angiographic exclusion criteria will be deemed eligible for Study Device Treatment.

#### 10.3.1. ENROLLMENT (INTENT-TO-TREAT)

A subject is defined as an intent-to-treat (ITT) patient and officially enrolled in the study once the Tack Endovascular System is advanced through the introducer sheath. Subjects in whom at least one Tack is not placed, will be exited after 12 months. Subjects in whom at least one Tack is placed will be followed for 36 months.

In addition, the per-protocol (PP) population will be defined as ITT subjects with evaluable data that have met the definition for device success, excluding subjects with major deviations such as:

- A major inclusion/exclusion criterion deviation; or
- A major procedural deviation

The criteria for deviations meeting the classification of “major” will be defined before study endpoint data is available for statistical analysis. All major deviations will be adjudicated by an independent designee without visibility to study results.

#### 10.3.2. TREATMENT RECOMMENDATIONS

The lesion considered for Tack placement is assessed with a minimum of two angiographic views, an anterior-posterior view and a 45 degree oblique view, for optimal visualization of the dissections. All dissections identified for treatment with the Tack will be categorized by type by the operator as described in **Section 10.2.1**. If there are no dissections present, the subject may not be enrolled and Tacks should not be placed.

Intact Vascular recommends deployment of a Tack to the distal edge of the target dissection. If additional Tack implants are required, the operator should continue proximally to the next planned deployment site. A minimum gap distance of 4.0mm between Tacks (end to end) is recommended. Overlapping Tack implants is not permitted.

Please refer to the Instructions for Use (IFU) for detailed instructions regarding recommended criteria for Tack Endovascular System placement.

#### 10.3.3. POST-STUDY DEVICE TREATMENT MEASUREMENTS

The following information should be recorded Post-Study Device Treatment:

- Device Success
- Number of Device Systems used to treat subject and associated lot numbers
- Number of Tacks Deployed
  - Ruler location of each deployed Tack (From distal to proximal to measure distance between Tacks)

- Number of Tacks deployed to treat each dissection identified in **Section 10.2.1**

#### 10.4. POST-DILATATION OF TREATED LESION (POST-STUDY DEVICE)

Post-dilatation of the target lesion is required in order to seat the anchors of the Tack.

##### 10.4.1. RECOMMENDATIONS

After Tack placement, it is recommended that post-dilatation of all deployed Tacks be performed using the following criteria.

- The balloon size for post-dilatation should use the largest balloon diameter used during angioplasty prior to Tack placement.
- Post-Dilatation Duration at Max Pressure: A minimum 120 seconds.
- Post-dilatation balloon angioplasty should be performed with a new standard balloon catheter (non-drug coated) to reduce the risk of contact with deployed Tacks while advancing the balloon catheter into place.

Please refer to the Instructions for Use (IFU) for detailed instructions regarding post-Tack placement balloon angioplasty recommendations.

##### 10.4.2. FINAL TREATMENT RESULTS

The following information should be recorded after post-dilatation and upon completion of index procedure:

- Details for balloon used for post-dilatation:
  - Type (standard or drug-coated), Length, Diameter
  - For each balloon inflation:
    - Inflation Duration(s) at Max Pressure
    - Max Pressure (ATM)
- Final residual diameter stenosis of target lesion treated with Tacks
- Bailout stent occurrence (post-study device treatment)
  - If applicable, bailout stent device details will be recorded
- Procedure time (defined as the time of insertion of introducer sheath to the time of withdrawal of last post-Tack dilatation PTA balloon catheter)
- Adverse event occurrence
- Procedural Success

#### 10.5. BAILOUT STENTING OF TARGET LESION (POST-STUDY DEVICE)

The use of a bailout stent may occur in the event of persistent flow-limiting dissection not able to be treated with the Tack (or as otherwise required for safety of the subject). All enrolled subjects in whom at least one Tack is placed and receive a bailout stent will be followed for the duration of the study.

## 11. POST-PROCEDURE/PRE-DISCHARGE

All subjects will be assessed prior to discharge (Pre-Discharge) and shall receive a medical regimen for the medications required post-procedure per **Table 6** in **Section 9.2**. All concomitant medications (antiplatelet/anticoagulant) shall be captured in the CRF.

### 11.1. REQUIRED ASSESSMENTS

Assessments required at pre-discharge include the following:

- Target limb resting ABI Measurement (within 72 hours post-index procedure)
- Adverse event occurrence
- Study medication assessment

All subjects receiving treatment with a Tack should be provided with the Tack Endovascular System Patient Implant Card (PIC). The PIC is designed for the patient to carry along with their insurance cards. This PIC is to be completed by the designated research personnel to include information pertaining to the Tack device(s) including the model, lot number and location of the implanted Tack(s) and the date of the index procedure. The card also provides manufacturing information and MRI Compatibility.

## 12. REQUIRED FOLLOW-UP VISITS AND ASSESSMENTS

All subjects will be required to return for clinic follow-up visits as outlined in **Table 5** of **Section 8.1** and in the sections below.

### 12.1. 30-DAY FOLLOW-UP VISIT (-2 DAYS / +14 DAYS POST-INDEX PROCEDURE)

The following assessments are required to be performed at the 30-day follow-up visit:

- Rutherford Classification
- Target limb resting ABI
- Duplex ultrasound
- Peripheral Artery Questionnaire (PAQ)
- EQ-5D-3L
- Walking Impairment Questionnaire (WIQ)
- Major adverse event (MAE) occurrence
- Adverse event occurrence
- Review of concomitant medications (antiplatelets/anticoagulants)

### 12.2. 6 MONTH FOLLOW-UP VISIT (±30 DAYS POST-INDEX PROCEDURE)

The following assessments are required to be performed at the 6 month follow-up visit:

- Rutherford Classification
- Target limb resting ABI
- Duplex ultrasound
- Peripheral Artery Questionnaire (PAQ)
- EQ-5D-3L
- Walking Impairment Questionnaire (WIQ)
- Major adverse event (MAE) occurrence
- Adverse event occurrence
- Review of concomitant medications (antiplatelets/anticoagulants)

### 12.3. 12 MONTH FOLLOW-UP VISIT ( $\pm 30$ DAYS POST-INDEX PROCEDURE)

The following assessments are required to be performed at the 12 month follow-up visit:

- Rutherford Classification
- Target limb resting ABI
- Duplex ultrasound
- X-Ray assessment
- Peripheral Artery Questionnaire (PAQ)
- EQ-5D-3L
- Walking Impairment Questionnaire (WIQ)
- Major adverse event (MAE) occurrence
- Adverse event occurrence
- Review of concomitant medications (antiplatelets/anticoagulants)

### 12.4. 24 MONTH FOLLOW-UP VISIT ( $\pm 30$ DAYS POST-INDEX PROCEDURE)

The following assessments are required to be performed at the 24 month follow-up visit:

- Rutherford Classification
- Target limb resting ABI
- Peripheral Artery Questionnaire (PAQ)
- EQ-5D-3L
- Walking Impairment Questionnaire (WIQ)
- Major adverse event (MAE) occurrence
- Adverse event occurrence
- Review of concomitant medications (antiplatelets/anticoagulants)

### 12.5. 36 MONTH FOLLOW-UP VISIT ( $\pm 30$ DAYS POST-INDEX PROCEDURE)

- The following assessments are required to be performed at the 36 month follow-up visit: Rutherford Classification
- Target limb resting ABI
- Peripheral Artery Questionnaire (PAQ)
- EQ-5D-3L
- Walking Impairment Questionnaire (WIQ)
- Major adverse event (MAE) occurrence
- Adverse event occurrence

#### 12.6. REVIEW OF CONCOMITANT MEDICATIONS (ANTIPLATELETS/ANTICOAGULANTS) DUPLEX ULTRASOUND (DUS) ASSESSMENT

Lower extremity arterial duplex ultrasonography is widely accepted as a method of determining arterial stenosis. Duplex ultrasonography combines spectral Doppler Technology in addition to B-mode imaging to allow the visualization of blood flow patterns within the arteries and veins. This spectral Doppler also provides a method to measure the velocity of the blood flow at specific locations.

The peak systolic blood flow velocity within the Tacks as well as the target vessel will be taken to determine the peak systolic velocity ratio (PSVR). All scheduled and unscheduled DUS exams shall be reviewed by an independent core laboratory for analysis.

The DUS exam should be performed on all subjects at the 30-day, 6, and 12 month follow-up visits. Duplex ultrasonography and/or angiography should be performed prior to any endovascular intervention during the follow-up period in order to assess the treated vessel patency. Operators should have experience with DUS and the specific methods for calculating the blood flow velocities. Operators will be trained on the DUS protocol provided by the respective core laboratory. Each operator is required to submit a test case DUS exam to the core lab prior to performing any study-required DUS exams.

A comprehensive overview for DUS acquisition requirements can be found in the core laboratory manual.

#### 12.7. X-RAY ASSESSMENT

An X-Ray assessment will be required at the 12 month follow-up visit to assess Tack integrity for all subjects in whom at least one Tack was placed during the index procedure.

- Acquire all x-rays as a high resolution image
  - Exposure < 80 kVp
  - Magnification of 1.5 image intensifier/receptor magnification
  - Avoid overlying bone and image entire Tacked segment(s)
- Make certain the radiopaque ruler is placed perpendicular to the imaging plane, flat on the patient. The ruler must be present in all film sequences to be analyzed. Once placed, the ruler should not be moved during the entire procedure.
- Use multiple acquisition views as defined in the x-ray protocol established by the core lab.

A comprehensive overview of procedural requirements for X-Ray assessments can be found in the core laboratory manual.

#### 12.8. UNSCHEDULED VISITS

A subject who presents to the investigational site between scheduled study-required follow-up visits for a target limb related adverse event or intervention to target limb is considered to have an “unscheduled visit”. Every effort should be made to gather data from the same clinical assessments required at the 12 month follow-up visit, including angiographic (if Target limb revascularization occurs), DUS and X-ray imaging (if clinically indicated or per standard of care). At the very least, target limb resting ABI measurement and Rutherford Classification should be assessed prior to any intervention to the target limb. In any case, if a Target limb intervention occurs, all the data from any assessment (clinical or imaging) performed prior to the intervention should be recorded in the Unscheduled Visit eCRF.

In the event a subject receives an intervention on the target vessel and/or lesion, all associated media (angiographic, DUS and X-Ray) shall be performed in accordance with imaging protocols and should be provided to the respective core labs. If a subject presents for target limb intervention that does not involve the target vessel/lesion, but the imaging performed captures the target lesion and Tacked portion vessel, such imaging should be sent to the respective core lab.

#### 12.9. FOLLOW-UP VISIT COMPLIANCE

As part of the informed consent process, all reasonable efforts will be made to obtain complete data for all subjects according to the follow-up visit schedule. Investigators and research staff will be expected to maintain continuous and open communication with study subjects regarding their participation in this study.

Three attempts via telephone will be made to contact subjects who do not present for study follow-up visits. If after three telephone attempts, the subjects cannot be contacted, a certified letter should be sent by the PI or designated study coordinator to the subject’s last known address. If possible, public records should be searched to ascertain survival status. If efforts to reach the subject are unsuccessful after three telephone contacts and a certified letter and there is no evidence of subject expiration, the sites will complete a Protocol Deviation for a Visit Not Done. A detailed record of all contact attempts should be maintained in the subject’s file. This process should be repeated for every subsequent follow-up visit and documented accordingly. These subjects will not be considered lost-to-follow-up (LTFU) and exited from the study until the end of the final follow-up visit window, unless it becomes known to the site that the subject has expired or wishes to withdraw consent.

#### 12.10. SUBJECT DISCONTINUATION AND REPLACEMENT

A subject may discontinue participation at any time without penalty or loss of benefits to which the subject is otherwise entitled. In addition, a subject may be discontinued if in the investigator’s opinion it is in the subject’s best interest. If a subject prematurely discontinues from the study, the reason will be recorded in the eCRF with supporting documentation. These results will be tabulated by number and percent for each category for discontinuation.

Subjects who prematurely exit the study after treatment will have their data maintained and evaluated up until the time of withdrawal. Subjects who are voluntarily or involuntarily (per PI discretion) withdrawn cannot re-enter the study. These subjects will not be replaced.

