#### 16.8. PRIMARY SAFETY OBJECTIVE

Subjects Included the Analysis: Subjects who meet the ITT definition as specified in **Section 16.2 and 10.3.1**.

Endpoint: Freedom from the occurrence of any new-onset major adverse event(s) (MAEs) defined as index limb amputation (above the ankle), CEC adjudicated clinically-driven target lesion revascularization (CD-TLR), or all-cause death at 30 days as specified in **Section 6.1**.

Hypothesis and Performance Goal: The VIVA performance goal of 88% will be used as the performance goal for this endpoint.

H0: Freedom from MAE (pMAE) is less than or equal to 88% at 30 days, pMAE ≤ 88%

H1: Freedom from MAE is greater than 88% at 30 days, pMAE > 88%

Sample Size Rationale: Using PASS 2012, a one-sample Exact Test, power = 90%, one-sided Type I error controlled at 5.0%, a performance goal of 88% and an assumed freedom from MAE at 30 days in Group 1 of 95%, 138 subjects with 30 days of follow-up and/or an MAE prior to 30 days are required for the analysis.

---

**Primary Statistical Analysis:** The primary statistical analysis will be conducted in subjects who meet the ITT definition and have observed data for the primary safety endpoint. The primary statistical method is a one-sample exact test comparing the proportion of subjects free from a MAE to the performance goal using a one-sided  $\alpha = 0.05$ . The exact one-sided 95% confidence interval for the proportion of subjects free from MAE will be calculated.

The freedom from MAE proportion will be calculated such that the numerator is the number of subjects in whom a MAE did not occur within 30 days of the index procedure. The denominator is the number of subjects with 30 days of follow-up plus the number of subjects with an MAE prior to 30 days who exited the study early, if any.

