Duplex Ultrasound (DUS)	A form of medical ultrasonography that includes the following elements on the same screen (“duplex”) to facilitate interpretation 1) B-mode, pulsed Doppler display to visualize the structure within a vessel and 2) Color-Doppler display to visualize the blood flow and hemodynamics within a vessel.
Index Procedure	The interventional procedure during which treatment with the Study Device occurs.
Intent-to-treat (ITT) subjects	A subject is defined as an intent-to-treat (ITT) patient and officially enrolled in the study once the Tack Endovascular System is advanced through the introducer sheath.
Luminal Patency	Restenosis <50% as determined by angiography or duplex ultrasound.
Major Adverse Event (MAE)	Index limb amputation (above the ankle), Clinically-driven target lesion revascularization, or All-cause death
Myocardial Infarction (MI)	Q wave MI (QWMI): requires one of the following criteria: 
 
• Chest pain or other acute symptoms consistent with myocardial ischemia and new pathological Q waves in two or more contiguous ECG leads
 
• New pathologic Q waves in two or more contiguous ECG leads and elevation of cardiac enzymes above normal.
 

	
Non-Q Wave MI (NQWMI): defined as either: elevated CK = 2X the laboratory upper limit of normal with the presence of an elevated CK-MB (any amount above the laboratory upper limit of normal) in the absence of new pathological Q waves or elevated CK-MB = 3X the laboratory upper limit of normal in the absence of new pathological Q waves.

Peak Systolic Velocity Ratio (PSVR)	
A measurement (using Duplex Ultrasonography) of peak velocity of blood (cm/sec) within a lesion or stented vessel segment that is divided by the peak velocity of blood (cm/sec) proximal to the lesion of stented segment.

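### Section 12.10 lets an investigator end observation of an already-treated subject, and such a subject, if exited before the endpoint with no recorded MAE or CD-TLR, drops out of that primary denominator

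*Combined protocol and SAP*

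**What the plan says.** **Exit (Section 12.10).** Besides the subject's own right to leave, "a subject may be discontinued if in the investigator’s opinion it is in the subject’s best interest". No criteria are listed. The section adds: "Subjects who are voluntarily or involuntarily (per PI discretion) withdrawn cannot re-enter the study. These subjects will not be replaced". On data it says: "Subjects who prematurely exit the study after treatment will have their data maintained and evaluated up until the time of withdrawal". It also requires documentation: "If a subject prematurely discontinues from the study, the reason will be recorded in the eCRF with supporting documentation", with reasons tabulated by category.

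**Missed visits (Section 12.9).** A subject who stops attending gets three telephone attempts and a certified letter. "If possible, public records should be searched to ascertain survival status". The subject is not treated as lost until the final visit window closes, barring death or withdrawal of consent.

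**Treatment (Sections 10.3.1 and 19).** Enrolment occurs when the device passes through the introducer sheath. The index procedure is "The interventional procedure during which treatment with the Study Device occurs".

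**Denominators.** For safety (16.8): "The denominator is the number of subjects with 30 days of follow-up plus the number of subjects with an MAE prior to 30 days", the latter being those who left early. For efficacy (16.9), a subject needs one of three things: a 12-month core-lab duplex finding, a CD-TLR before the 12-month window closes, or a later patent duplex with no intervening CD-TLR. An angiogram in the 12-month window replaces the duplex.

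**Missing data (16.6).** Best-case, worst-case and tipping-point analyses are planned in the ITT sample.

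**The concern.** Because the study device is given once, an investigator who discontinues a subject later withholds no further device treatment; only follow-up ends. Post-procedure antiplatelet therapy is a recommendation (Table 6) and does not depend on remaining in the study. The protocol nevertheless pursues a subject who merely misses visits harder than one whom the investigator has exited, although the latter may be reachable and may not have refused anything.

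The study is single-arm and open-label, and both primary tests use observed data. If exits relate to prognosis, the observed rates rise, and no control arm shares the distortion. Well-meant withdrawal of a deteriorating subject would have the same effect as any other selective loss.

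**Working it through.** **1. Who leaves a denominator**

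| State at exit | Safety (16.8) | Efficacy (16.9) |
|---|---|---|
| MAE recorded before day 30 | Counted as failure | Counted as failure if the MAE is a CD-TLR |
| CD-TLR recorded before the 12-month window closes | Counted as failure if before day 30 | Counted as failure |
| Exit before day 30, no MAE or CD-TLR | Not counted | Not counted |
| Exit after day 30 and before the 12-month duplex, no CD-TLR | Counted | Not counted |

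The last two rows are the exposure. They include a subject with worsening symptoms or a non-patent 6-month duplex. Section 16.6 mentions using an earlier duplex, but the rule in 16.9 uses only a later patent one; the two sections should be reconciled.

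**2. The plan's own figures**

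Inputs from 16.3, 16.8 and 16.9:
- Efficacy: goal 53%, assumed patency 65%, one-sided α 0.025, 178 evaluable.
- Safety: goal 88%, one-sided α 0.05.
- Attrition 15%, 210 enrolled.

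Exact test: r is the smallest count with P(X ≥ r | n, goal) ≤ α.
- Efficacy at n = 178: r = 108, attained α 0.0237, power at 65% = 0.900. This reproduces the plan.
- Enrolment: 178 / 0.85 = 209.4, rounded up to 210. This also reproduces.

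**3. Effect of selective exits on type I error**

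Let all N = 210 treated subjects have a true rate equal to the goal, and let k who would have failed be exited unrecorded. The success count is still X ~ Bin(210, goal), but the test uses n = 210 − k with its own threshold r. Type I error = P(X ≥ r | 210, goal). The model has no other losses. The documents give no k, so a range is shown.

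| k | Efficacy r | Efficacy error (limit 0.025) | Safety r | Safety error (limit 0.05) |
|---|---|---|---|---|
| 0 | 126 | 0.024 | 193 | 0.046 |
| 1 | 126 | 0.024 | 192 | 0.073 |
| 2 | 125 | 0.034 | 192 | 0.073 |
| 3 | 125 | 0.034 | 191 | 0.110 |
| 5 | 124 | 0.045 | – | – |
| 10 | 121 | 0.101 | – | – |

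The steps reflect the discreteness of the exact test.

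**4. Effect on a given efficacy result**

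Exact one-sided p against 53%:
- Smallest passing result: 108/178, p = 0.0237. One failure added back: 108/179, p = 0.0289, which fails.
- Planned result: 0.65 × 178 = 115.7, so 116/178, p = 0.0007. Fourteen failures added back: 116/192, p = 0.0231, which passes. Fifteen: 116/193, p = 0.0280, which fails.

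**5. What the sensitivity analyses can settle**

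With 116/178 patent and 210 − 178 = 32 missing:
- Worst case: 116/210, p = 0.28.
- Tipping point: significance is lost when the 23rd of the 32 is counted as a failure (116 + 9 = 125 successes in 210, p = 0.034).
- At 65% true patency in 178 evaluable subjects, the worst case stays significant with probability P(X ≥ 126 | 178, 0.65) = 0.06.

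**The case against.** The discretion is limited. It is tied to the subject's best interest, reasons are documented and tabulated, and Section 16.7 has early exits summarized. MAEs are reportable within two business days (14.4.1), and a target-limb presentation before exit falls under the unscheduled-visit rules (12.8). Section 16.6 already contains an analysis that counts every missing subject as a failure. All of this stands and narrows the point.

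Four stronger readings are tempting, and the documents do not support them:

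- **That all data collection stops at exit.** This is the plain reading of 12.10 but is not stated in those words. Section 12.9 opens with a general aim of complete data for every subject, Section 14 has adverse events followed to resolution or stability, and the consent form, which might address later data use, is not in the material reviewed.
- **That subjects doing badly generally escape the analysis.** Those with a recorded MAE before day 30, or a CD-TLR before the 12-month window closes, remain failures. Nothing in the documents suggests that investigators would exit symptomatic subjects.
- **That one withdrawal would reverse the trial.** This is true only at the smallest passing count, where one added failure tips the result by construction.
- **That the 15% attrition allowance (32 of 210) measures investigator exits.** It covers loss from every cause.

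A practical objection also stands. CD-TLR as defined in Section 19 needs angiographic stenosis, a Rutherford increase and an ABI fall, so a telephone call cannot establish it. Adding failures found in records while event-free subjects stay missing would bias 16.9 downwards.

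**Conclusion.** The concern holds in limited form. As written, 12.10 permits the investigator to end observation of a treated subject, and 16.8 and 16.9 then omit that subject if no qualifying event or endpoint assessment was recorded. The loss can be related to outcome, and the 16.6 analyses show its possible reach without supplying the outcome.

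The size depends on an unknown number of exits. For efficacy, two selectively exited would-be failures are enough to exceed the nominal 0.025 when true patency equals the goal, yet a result at the planned rate would tolerate 14. Safety is more sensitive per subject, since one is enough to exceed 0.05, but only exits before day 30 matter and these are probably few. The error rates assume that every removed subject would have failed, which is the unfavourable extreme. This is a worthwhile, inexpensive improvement to follow-up, not a demonstrated bias in either endpoint.

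**What to change.** In Section 12.10:

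- Separate withdrawal of consent from the investigator's discontinuation of study assessments. Keep subjects of the second kind in the study unless they withdraw consent.
- Apply the 12.9 contact and public-record steps to them.
- With consent, collect through the 12-month window: vital status, target-limb amputation, source records of any target-lesion revascularisation, and any target-limb duplex or angiogram. Still seek the 12-month duplex where the subject agrees.

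In the analysis sections:

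- Count deaths and amputations in 16.8.
- Count a revascularisation only when the CEC can adjudicate it as CD-TLR from source records.
- Count core-lab-read 12-month imaging in 16.9 on the same terms whether patent or not, so that recovered data add successes as well as failures.
- Leave whatever remains missing to the 16.6 analyses.

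The cost is protocol and consent wording, modest site work for what should be a small number of subjects, and a possibly less favourable observed rate.
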